### Safety Results of Phase 1 IVACFLU-S Seasonal Flu Vaccine Trial

The safety results can be summarized as follows:

No local or systemic solicited AEs were reported within 30 minutes after vaccination. All participants were observed to have oral temperature with in normal range (<37.7°C; Grade 0) Overall, 20 participants (66.7 %) on vaccine and 8 participants (26.7%) on placebo, reported at least 1 local solicited AE on Day 1. Among vaccine recipients who experienced local reactions, pain and tenderness at the injection site were the most common reaction (Table 3). Majority were assessed as mild and resolved spontaneously within 24-48 hours and. By day 7, only 1 participant (3.3%) on placebo reported at least 1 local solicited AE. In contrast no participant on vaccine reported any local solicited AE beyond day 4 [7].

No participant reported fever (oral temperature >37.7°C). Overall, the number of participants who reported any systemic solicited AEs at Day 1 and their severity were similar across vaccine and placebo groups (8 participants [26.7%] on vaccine and 7 participants [23.3%] on placebo). The majority of systemic solicited AEs reported by participants on vaccine were mild (Table 3) and none lasted beyond 6 days. In contrast in the group randomized to placebo, 2 participants reported severe reactions (fatigue and joint ache) and 3 participants reported multiple solicited systemic adverse events up to Day 7 (Figure 5).

[figure not shown]
There were no deaths, SAEs, or discontinuation due to AEs reported in the study. There were no clinically significant abnormalities observed in the clinical laboratory results or product-related trends based on a review of the mean and median laboratory values at each scheduled evaluation, vital signs, and physical examination evaluations during the study (data not shown). The incidence of unsolicited AEs (Table 4) were similar across vaccine and placebo groups (7 participants [23.3%] each). All unsolicited AEs reported in the study were mild in intensity and were considered to be not related to the investigational product by the Principal Investigator.

Overall the vaccine was safe and well tolerated with a safety profile similar to licensed seasonal influenza vaccine.

**Table 3: Summary of Solicited Local and Systemic Adverse Events for Vaccine and placebo Recipients Occurring from Day 1-7 After Vaccination Based on Most Severe Symptom Reported**

Solicited Adverse Event	Vaccine (N=30)			Placebo (N=30)		

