### **8.2.2 Seventh Day after Injection (Day 8 ± 1)**

1. Study staff will confirm participant identity.
2. Study staff will review the participant Diary Card and interim history with the participant and inquire about any new medical events since medical histories were last updated. Any AEs that have occurred and meet reporting requirements, will be recorded in the appropriate section(s) of the CRF. Diary Card information will be entered into the database.
3. The participant will have temperature, pulse rate, and blood pressure recorded. A study clinician will perform a targeted (symptom based) physical examination and record the information Results will be reviewed by study staff and with the participant.
4. The participant will be instructed to inform the investigator as soon as possible if he/she experiences an AE requiring medical care and to seek medical care as appropriate. If the participant visits a health care provider, the participant should be sure to inform the

health care provider of participation in this study and give the health care provider the contact information for the investigator.

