### 9.1.3 Physical Examination

#### General Physical Examinations

Qualified study clinicians will conduct a physical examination of all participants at S1/D1. This physical examination will include the following:

- Recording of general appearance
- Physical examination of all organ systems. This includes the following:
  - neurologic examination, including cranial nerve examination
  - chest auscultation
  - examination of lymph nodes (axillary and cervical)
  - heart auscultation
  - abdomen palpation (to check for liver size)
- Measurement of the following vital signs:
  - body temperature
  - blood pressure
  - pulse/heart rate

\* Grade 1 elevated blood pressure (140 to < 160 mmHg systolic OR 90 to < 100 mmHg diastolic) will not be considered to be exclusionary at screening, unless judged to be clinically significant by the PI.

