#### Targeted Physical Examination

The targeted Physical examination focuses on symptoms reported by the participant and the presence or absence of local and systemic reactogenicity. If no symptoms are reported by the participant, the Targeted PE does not need to be performed. The exam will be made by a clinician on Day 1 (only if D1 is on a different day from S1) and Day 8. Evaluation must be made prior to administration of injection of study product if done on Day 1.

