### 13.3 Safety

There will be 740 subjects randomized to IVACFLU-S arm in the phase 2/3 study; with account of 5% drop-out rate; there would be at least 700 evaluable participants for safety analysis. If no vaccine-related serious adverse events are observed in 700 vaccine recipients, study would be able to exclude events occurring at approximately 0.43% based on the upper bound of the one-sided 95% Confidence Interval (CI) using the Clopper-Pearson method. The probability of observing at least one vaccine-related serious adverse event in 700 subjects is 90% and >95% if the true rate of such events is 0.33% and 0.43% respectively. The precision of the estimate of AEs judged to be related to IVACFLU-S as bounded by 95% CI is presented in Table 16.

However, the full analysis population will be used for safety analysis, not the assumed number of 700 evaluable subjects.

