2. Body temperature (oral) [Body temperature]		
[VSTEMPCMP1] [VSTEMP1] xx.x °C[b] [VSTEMPF] Finding [A:1]  Normal [A:2]  Abnormal, NCS [A:3]  [VSTEMP1GR] Abnormal, CS Grading Scale [A:0]  Ungradable [A:1]  1 (38.0 - <38.6°C) [A:2]  2 (38.6 - <39.3°C) [A:3]  3 (39.3 - <40.0°C) [A:4]  4 (≥ 40.0°C)

3. Blood Pressure [Blood Pressure]		
[VSBPCMP2] [VSBPCMP1] [SYSBP1] [DIABP1] N3 mmHg[b] N3 mmHg[b] Systolic Diastolic [VSBPF] Finding [A:1]  Normal [A:2]  Abnormal, NCS [A:3]  [VBBPG1] Abnormal, CS Grading Scale [A:0]  Ungradable [A:1]  1 140 to < 160 mmHg systolic OR 90 to < 100 mmHg diastolic [A:2]  2 ≥ 160 to < 180 mmHg systolic OR ≥ 100 to < 110 mmHg diastolic [A:3]  3 ≥ 180 mmHg systolic OR ≥ 110 mmHg diastolic [A:4]  4 Life Threatening

4. Pulse Rate [Pulse Rate]		
[VSHRCMP1] [VSHR1] N3 beats/min[b] [VSHRF] Finding [A:1]  Normal [A:2]  Abnormal, NCS [A:3]  [VSBPSP1] Abnormal, CS Specify: A200*

Targeted Physical Examination [TPE2SC]		
5. Physical examination is not required unless subject reports symptoms. Did the subject have any symptoms that required evaluation? [Did the subject have any symptoms that required evaluation?]		
[PETVSYN1] [A:1]  Yes [A:2]  No If Yes, please complete Abnormal Findings below.

6. 	PE number	Area/System
Abnormal Findings Entry [TPE3SC]		
6.1 PE number [read-only] [PE number]		
[TPENUM] N3

6.2* Area/System [Area/System]		
[TPESYSPD] [A:1]  [TPESYS] [c]TPESYS [v] [A:2]  [TPEDESOTH] Other, specify: A200*

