Full description of treatment groups / treatment sequences	1 = IVACFLU-S 2 = PLACEBO
Ratio of subjects to treatment groups / treatment sequences	IVACFLU-S : PLACEBO: 5:1

Document: \\quintiles.net\Enterprise\Sites\gbthv\QTHVRANDOM\IVAC\IVACFLU-S-0203\03 Rando specification\IVACFLU-S-0203\_RandoSpec\_BLI\_NDED\_2017\_03\_31\_v2\_0  
Author: [name] Version Number: 2.0  
Version Date: 31MAR2017

Template No: CS\_TP\_BS025 Revision 5  
Effective Date: 01Nov2016

Reference: CS\_WI\_BS002

Copyright © 2009, 2010, 2011, 2014, 2016 QuintilesIMS. All rights reserved.  
The contents of this document are confidential and proprietary to Quintiles IMS Holdings, Inc. and its subsidiaries.  
Unauthorized use, disclosure or reproduction is strictly prohibited.

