N= Total number of subjects in the relevant population per by-group stratification level, n= Number of subjects with available response under each group at both time points, % = Calculated relative to the total number of subjects have measurable assessment for analysis in each group at both visit  
Programming Note: Add Total Column also i.e., in addition to Vaccine and Placebo.

Source Data: Listing 16.2.8.3

Document: \\EEDC-NAS01A\Biosdata\Path\IVACFLU-S\YA06804\Biostatistics \Documentation\SAP\IVACFLU-S-0203\_Mock\_Tables\_V1.0

Author: [name]

Version Number:

1.0

Version Date:

11AUG 2017]

Template No: CS\_TP\_BS016 Revision 4

Reference: CS\_WI\_BS005

Effective Date: 01Apr2016

Copyright © 2009, 2010, 2012, 2016 Quintiles Transnational Corp. All rights reserved.

The contents of this document are confidential and proprietary to Quintiles Transnational Corp. Unauthorized use, disclosure or reproduction is strictly prohibited.

ANNOTATED SHELLS

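### Table 14.3.7.1 takes percentages of participants assessed at both baseline and Day 8, although the Day 8 examination is required only if symptoms are reported; the shell also cannot show a new abnormal finding

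*Combined protocol and SAP*

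**What the plan says.** **Baseline examination.** Protocol 9.1.3 and SAP 17.6 both state: "Qualified study clinicians will conduct a physical examination of all participants at S1/D1".

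**Day 8 examination.** The same two sections state: "If no symptoms are reported by the participant, the Targeted PE does not need to be performed". Item 5 of the eCRF Targeted PE form carries the rule, "Physical examination is not required unless subject reports symptoms", and then asks whether there were symptoms that needed evaluation. Protocol 8.2.2 describes the visit as: "A study clinician will perform a targeted (symptom based) physical examination and record the information". It places the diary and interim history review before the examination, and it has temperature, pulse and blood pressure recorded without any condition.

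**The table.** Shell 14.3.7.1 is headed Full Analysis Population and carries that N for each arm. Its percentages, however, are "Calculated relative to the total number of subjects have measurable assessment for analysis in each group at both visit". The only baseline rows and Day 8 columns are abnormal not clinically significant (NCS) and abnormal clinically significant (CS). Its source is Listing 16.2.8.3, which lists abnormal findings.

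**The default.** SAP section 6 takes percentages of participants in the analysis set who have data, unless stated otherwise, so the footnote follows the general rule.

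**The concern.** Because everyone is examined at baseline, Day 8 alone decides who has an assessment at both visits. For vital signs the same kind of footnote does little harm, since every Day 8 attendee is measured. For the physical examination, missing data are planned: they mean that the participant reported no symptoms. Symptoms arise after randomisation and can depend on the arm. A percentage on that base is therefore not a randomised comparison, although the shell sets the arms side by side under the Full Analysis N.

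The layout adds a second problem. With no 'Normal' category, the table shows only participants who were already abnormal before vaccination. A finding that first appears after vaccination, which is what a safety shift table is mainly read for, has no cell to go in.

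**Working it through.** The shell holds placeholders only, so there is no printed figure to reproduce. The check is what the base does to a percentage.

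**Inputs**
- Vaccine N = 740. Protocol 13.3: "There will be 740 subjects randomized to IVACFLU-S arm in the phase 2/3 study".
- Placebo N = 148. The Randomization Specification gives "IVACFLU-S : PLACEBO: 5:1"; 888 × 5/6 = 740 and 888/6 = 148.
- Phase 1 local reactions on Day 1 (protocol 2.1.6): "20 participants (66.7 %) on vaccine and 8 participants (26.7%) on placebo, reported at least 1 local solicited AE on Day 1".
- Phase 1 systemic reactions on Day 1 (same section): 8/30 = 26.7% vaccine, 7/30 = 23.3% placebo.
- Phase 1 symptoms late in the first week (same section): on vaccine, no local reaction beyond Day 4 and no systemic reaction lasting beyond 6 days; on placebo, 1 participant with a local reaction by Day 7 and 3 with multiple systemic events up to Day 7.

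**Formula.** For any cell of the table, let r be the share of the arm's Full Analysis participants in that cell and s the share examined at Day 8. On the examined base the printed percentage is r/s. The printed vaccine-to-placebo ratio is then

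(rV/rP) × (sP/sV),

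so the base multiplies the ratio by sP/sV. The documents give no Day 8 examination shares and no finding rates. Every s and r below is an assumption, with r equal in the two arms.

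| Assumed meaning of symptoms | sV | sP | Examined V / P | r | Printed V / P | Factor sP/sV |
|---|---|---|---|---|---|---|
| Any local reaction (Day 1 rate) | 66.7% | 26.7% | 493 / 39 | 2% | 3.0% / 7.5% | 0.40 |
| Any systemic reaction (Day 1 rate) | 26.7% | 23.3% | 197 / 35 | 2% | 7.5% / 8.6% | 0.88 |
| Still present at Day 7-8 | 3.3% | 3.3% | 25 / 5 | 1% | 30% / 30% | 1.0 |
| Still present at Day 7-8 | 1.7% | 3.3% | 12 / 5 | 1% | 60% / 30% | 2.0 |
| Still present at Day 7-8 | 3.3% | 10% | 25 / 15 | 1% | 30% / 10% | 3.0 |
| Still present at Day 7-8 | 2.0% | 10% | 15 / 15 | 1% | 50% / 10% | 5.0 |

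On a Full Analysis base every row would print equal percentages in the two arms (2% or 1%), whatever the examination shares.

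**Direction.** A factor below 1 favours vaccine and a factor above 1 goes against it, and both occur. Even at 0.40, vaccine prints lower only while rV/rP is below 0.667/0.267 = 2.5. At 6% against 2% it prints 6/0.667 = 9.0% against 2/0.267 = 7.5%.

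**Which base is meant.** The footnote does not define a measurable assessment. Three readings are open:
- Those actually examined at Day 8. This is the natural reading, and the one in the table above.
- All Day 8 attendees, if a No on eCRF item 5 counts as an assessment. Then there is no selection.
- Those with abnormal entries at both visits, because the source listing holds only abnormal findings. This base is narrower still.

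**The case against.** **The tempting stronger reading.** A reader might infer that the base flatters the vaccine: vaccine causes more reactions, so more vaccinees are examined, the denominator grows and the percentage falls. Applying the Day 1 local reaction rates as examination shares gives the 0.40; using the pain rates for another manufacturer's vaccine in protocol Table 13 (55% against 12%, within 4 days of vaccination) gives 0.12/0.55 = 0.22. The documents do not support this. Those rates are not Day 8 examination rates. The Phase 1 account that supplies the Day 1 figures also reports that late first-week symptoms were on placebo, and Day 1 systemic rates were nearly equal. The eCRF trigger is symptoms that needed evaluation, while most Phase 1 local reactions were mild and resolved in 24-48 hours. Nor do the figures measure hidden new findings, because the shell counts only participants already abnormal at baseline.

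**The case that nothing needs changing.** The Targeted PE form is a standard Day 8 form that also holds the vital signs, so a No on symptoms may already count as an assessment. The footnote follows the SAP default. The table has no test and is not an endpoint, and its counts sit under the Full Analysis N, so a reader can compute n/N. Clinically significant Day 8 findings must carry an adverse event number on the eCRF, and adverse events are tabulated on the Full Analysis population.

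**What stands.** These arguments limit the importance, and the first could remove the selection if the plan said so. It does not say so. The adverse event link does not cover abnormal findings judged not clinically significant, which this shell also reports, and no reading of the base supplies the missing 'Normal' category.

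**Conclusion.** The point holds, as a minor one. Unless an entry of no symptoms counts as an assessment, the percentages in Table 14.3.7.1 rest on a symptom-selected subset formed after randomisation and cannot be compared between arms. The direction and size of the bias are unknown: the factors of 0.40 to 5.0 show how far the result depends on assumed examination shares and are not an estimate for this trial. If only current symptoms lead to an examination, the placebo base could be about 5 to 15 people (3.3% to 10% of 148, assumed), too few for a stable percentage.

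Separately, and on any reading of the base, the shell cannot show a change from normal to abnormal.

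The conclusion on comparability rests on the natural reading of the footnote and on findings being recorded only in those examined.

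**What to change.** In Table 14.3.7.1 and its footnote:
- base the percentages on all Full Analysis participants with a Day 8 visit in each arm;
- show the number actually examined at Day 8 per arm on its own line;
- add a 'Normal' row and column, as Table 14.3.6.3 already has for vital signs, and a Day 8 category 'Not examined (no symptoms reported)'.

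No new data are needed: the eCRF records whether the targeted examination was done and whether symptoms required evaluation. The source must extend beyond the abnormal-findings listing so that normal and unexamined participants can be counted.

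The cost is the layout and footnote of one shell. The small downside is that an unreported, silent finding in an unexamined participant is counted as absent, which already follows from the examination rule. The examination rule itself need not change.

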### MODIFICATION HISTORY

Unique Identifier for this Version	Date of the Document Version	Author	Significant Changes from Previous Authorized Version
		[name]	Not applicable. First version.

---

Document: \\IEEDC-NAS01A\Biosdata\Path\IVACFLU-S\IYA06804\Biostatistics \Documentation\SAP\IVACFLU-S-0203\_Mock\_Listings\_V1.0  
Author: [name]  
Version Number: 1.0  
Version Date: [11AUG2017]

Template No: CS\_TP\_BS016 Revision 4  
Effective Date: 01Apr2016

Reference: CS\_WI\_BS005

Copyright © 2009, 2010, 2012, 2016 Quintiles Transnational Corp. All rights reserved.  
The contents of this document are confidential and proprietary to Quintiles Transnational Corp. Unauthorized use, disclosure or reproduction is strictly prohibited.

TABLE AND LISTING MOCK SHELL

---

The contents of this document are confidential and proprietary to Quintiles Transnational Corp. Unauthorized use, disclosure or reproduction is strictly prohibited.

TABLE AND LISTING MOCK SHELL

Listing 16.1.1.1  
Eligibility Criteria  
All subjects

Subject ID/ Site ID/ Age Group	Consent Given (Yes/No)	Date of Informed Consent/Study Day	Met Eligibility (Yes/No)	If Not Met, Specification (eCRF)
Xxxxx/ xxxx/ xxxx	Yes	DDMMYYYY	Yes	
xxxxx/ xxxx/ xxxx	Yes	DDMMYYYY	No	Refused to come for screening
xxxxx/ xxxx/ xxxx	Yes	DDMMYYYY	Yes	
xxxxx/ xxxx/ xxxx	Yes	DDMMYYYY	Yes	

Study day: Derived relative to administration date/time of vaccination.

Programming Note: Sort by Subject ID.

Document: \\IEEDC-NAS01A\Biosdata\Path\IVACFLU-S\IYA06804\Biostatistics \Documentation\SAP\IVACFLU-S-0203\_Mock\_Listings\_V1.0  
 Author: [name]  
 Version Number: 1.0  
 Version Date: [11AUG2017]

Template No: CS\_TP\_BS016 Revision 4  
Effective Date: 01Apr2016

Reference: CS\_WI\_BS005

Copyright © 2009, 2010, 2012, 2016 Quintiles Transnational Corp. All rights reserved.  
The contents of this document are confidential and proprietary to Quintiles Transnational Corp. Unauthorized use, disclosure or reproduction is strictly prohibited.

TABLE AND LISTING MOCK SHELL

Listing 16.2.1.1  
Subject Disposition  
All subjects

Treatment	Subject ID/ Site ID/ Age Group	Subject Study Status	Completion/ Discontinuation Date Study Day	Reason for Discontinuation	Other/AE/SAE/Specification (eCRF)
Vaccine	xxxxx/ xxxx/ xxxx	Completed	DDMMYYYY		
Vaccine	xxxxx/ xxxx/ xxxx	Completed	DDMMYYYY		
Placebo	xxxxx/ xxxx/ xxxx	Completed	DDMMYYYY		
Placebo	xxxxx/ xxxx/ xxxx	Discontinued	DDMMYYYY	Other	xxxxxxxxxxxxxxxx

AE: Adverse Event. SAE: Serious Adverse Event.  
Study day: Derived relative to administration date/time of vaccination.

Programming Note: Sort by Treatment and Subject ID

Document: \\IEEDC-NAS01A\Biosdata\Path\IVACFLU-S\IYA06804\Biostatistics \Documentation\SAP\IVACFLU-S-0203\_Mock\_Listings\_V1.0  
 Author: [name]  
 Version Number: 1.0  
 Version Date: [11AUG2017]

Template No: CS\_TP\_BS016 Revision 4  
 Effective Date: 01Apr2016  
 Reference: CS\_WI\_BS005

Copyright © 2009, 2010, 2012, 2016 Quintiles Transnational Corp. All rights reserved.  
 The contents of this document are confidential and proprietary to Quintiles Transnational Corp. Unauthorized use, disclosure or reproduction is strictly prohibited.

TABLE AND LISTING MOCK SHELL

Listing 16.2.1.2  
Subject Randomization  
Enrolled Population

Subject ID/ Site ID/ Age Group	Subject Randomized (Yes/No)	Date of Randomization/Study Day	Randomization Number	Treatment Description	Reason If Not Randomized
xxxxx/ xxxx/ xxxx	Yes	DDMMYYYY/ xx	xxxxx	Vaccine	
xxxxx/ xxxx/ xxxx	No		xxxxx		Lost to follow-up
xxxxx/ xxxx/ xxxx	Yes	DDMMYYYY/ xx	xxxxx	Placebo	
xxxxx/ xxxx/ xxxx	Yes	DDMMYYYY/ xx	xxxxx	Placebo	

Study day: Derived relative to administration date/time of vaccination.

Programming Note: Sort by Subject ID.

Document: \\IEEDC-NAS01A\Biosdata\Path\IVACFLU-S\IYA06804\Biostatistics \Documentation\SAP\IVACFLU-S-0203\_Mock\_Listings\_V1.0  
Author: [name]  
Version Number:  
Version Date:

1.0  
[11AUG2017]

Template No: CS\_TP\_BS016 Revision 4  
Effective Date: 01Apr2016

Reference: CS\_WI\_BS005

Copyright © 2009, 2010, 2012, 2016 Quintiles Transnational Corp. All rights reserved.

The contents of this document are confidential and proprietary to Quintiles Transnational Corp. Unauthorized use, disclosure or reproduction is strictly prohibited.

TABLE AND LISTING MOCK SHELL

Listing 16.2.1.3  
 Subject Population  
 Enrolled Population

Treatment	Subject ID/ Site ID/ Age Group	All Enrolled Population	Full Analysis Population	Per-Protocol Population	Reason for Exclusion from the population
Vaccine	xxxxx/ xxxx/ xxxx	Yes	Yes	Yes	xxxxxxxxxxxxxxxxxxxx
Vaccine	xxxxx/ xxxx/ xxxx	Yes	No	No	xxxxxxxxxxxxxxxxxxxx

Programming Note: Sort by Treatment and Subject ID

Document: \\EEDC-NAS01A\Biosdata\Path\IVACFLU-S\IYA06804\Biostatistics \Documentation\SAP\IVACFLU-S-0203\_Mock\_Listings\_V1.0  
 Author: [name]  
 Version Number: 1.0  
 Version Date: [11AUG2017]

Template No: CS\_TP\_BS016 Revision 4  
 Effective Date: 01Apr2016

Reference: CS\_WI\_BS005

Copyright © 2009, 2010, 2012, 2016 Quintiles Transnational Corp. All rights reserved.  
 The contents of this document are confidential and proprietary to Quintiles Transnational Corp. Unauthorized use, disclosure or reproduction is strictly prohibited.

TABLE AND LISTING MOCK SHELL

Listing 16.2.2.1  
Protocol Deviations  
Full Analysis Population

Site ID: xxxxxx

---

Treatment	Subject ID/ Site ID/ Age Group	Category	Severity	Protocol Deviation Term	Deviation Description
Vaccine	xxxxx/ xxxx/ xxxx	Informed Consent Criteria	Critical	xxxxxxxxx	xxxxxxxxx

---

Potential Protocol Deviations for the study and categorize according to the pre-defined categories within the Clinical Trial Management System (CTMS).

Programming Note: Sort by Treatment and Subject ID

---

Document:	\\EEDC-NAS01A\Biosdata\Path\IVACFLU-S\IYA06804\Biostatistics \Documentation\SAP\IVACFLU-S-0203_Mock_Listings_V1.0	Version Number:	1.0
Author:	[name]	Version Date:	[11AUG2017]

Template No: CS\_TP\_BS016 Revision 4  
Effective Date: 01Apr2016

Reference: CS\_WI\_BS005

Copyright © 2009, 2010, 2012, 2016 Quintiles Transnational Corp. All rights reserved.  
The contents of this document are confidential and proprietary to Quintiles Transnational Corp. Unauthorized use, disclosure or reproduction is strictly prohibited.

TABLE AND LISTING MOCK SHELL

Listing 16.2.4.1  
Demographics and Baseline Characteristics  
Enrolled Population

Treatment	Subject ID/ Site ID/ Age Group	Date of Birth/ Age(Years)	Sex	Ethnicity	Child Bearing Potential [a]	Urine Pregnancy Test Result[a]
Vaccine	xxxxx/ xxxx/ xxxx	DDMMYYYY/ xx	Male	Kinh	Yes	Negative

[a]: Applicable only for female subjects.

Programming Note: Sort by Treatment and Subject ID.

Document: \\EEDC-NAS01A\Biosdata\Path\IVACFLU-S\IYA06804\Biostatistics \Documentation\SAP\IVACFLU-S-0203\_Mock\_Listings\_V1.0  
Author: [name]  
Version Number: 1.0  
Version Date: [11AUG2017]

Template No: CS\_TP\_BS016 Revision 4  
Effective Date: 01Apr2016

Reference: CS\_WI\_BS005

Copyright © 2009, 2010, 2012, 2016 Quintiles Transnational Corp. All rights reserved.  
The contents of this document are confidential and proprietary to Quintiles Transnational Corp. Unauthorized use, disclosure or reproduction is strictly prohibited.

TABLE AND LISTING MOCK SHELL

Listing 16.2.4.2  
Current Medical Condition  
Full Analysis Population

Treatment	Subject ID/ Site ID/ Age Group	System Organ Class/ Preferred Term/Verbatim Term [a]	Condition	Medication Taken for this Current Condition (Yes/No)
Vaccine	xxxxx/ xxxx/ xxxx	xxxx/ xxxxxx/ xxxxxxxx	xxxxx	No
Placebo	xxxxx/ xxxx/ xxxx	xxxx/ xxxxxx/ xxxxxxxx	xxxxx	Yes

e-CRF: Electronic Case Report Form. MedDRA: Medical Dictionary for Regulatory Activities.  
[a]: Medical History terms (including other systems): Coded using MedDra version 20.0.

Programming Note: Sort by Treatment, Subject ID and SOC

Document: \\EEDC-NAS01A\Biosdata\Path\IVACFLU-S\IYA06804\Biostatistics \Documentation\SAP\IVACFLU-S-0203\_Mock\_Listings\_V1.0  
Author: [name]  
Version Number: 1.0  
Version Date: [11AUG2017]

Template No: CS\_TP\_BS016 Revision 4  
Effective Date: 01Apr2016

Reference: CS\_WI\_BS005

Copyright © 2009, 2010, 2012, 2016 Quintiles Transnational Corp. All rights reserved.  
The contents of this document are confidential and proprietary to Quintiles Transnational Corp. Unauthorized use, disclosure or reproduction is strictly prohibited.

TABLE AND LISTING MOCK SHELL

Listing 16.2.4.3  
Concomitant Medication  
Full Analysis Population

Treatment	Subject ID/ ID/Age Group	Site	Medication Name	Start Date/ Date/Study	Stop Day	Ongoing	Dose/Unit/ Frequency	Route of Administration	Indication	Specification (eCRF)	
Vaccine	xxxxx/	xxxx/	xxxx	xxxxx	DDMMYYYY/ DDMMYYYY/	xx	No	Xx/xx/xx	Oral	Unsolicited AE	xxxxxxx
Vaccine	xxxxx/	xxxx/	xxxx	xxxxx	DDMMYYYY/ DDMMYYYY/	xx	No	Xx/xx/xx	xxxx	xxxxxxx	xxxxxxx
Vaccine	xxxxx/	xxxx/	xxxx	xxxxx	DDMMYYYY/ DDMMYYYY/	xx	No	Xx/xx/xx	xxxx	xxxxxxx	xxxxxxx

AE: Adverse Event.  
Study day: Derived relative to administration date/time of vaccination.  
Concomitant medication: Defined as medication started on or after the day of vaccination or were ongoing on the date of vaccination or ended on or after the vaccination.

Programming Note: Sort by Treatment Subject ID and Start date.

Document: \\IEEDC-NAS01A\Biosdata\Path\IVACFLU-S\IYA06804\Biostatistics \Documentation\SAP\IVACFLU-S-0203\_Mock\_Listings\_V1.0  
Author: [name]  
Version Number: 1.0  
Version Date: [11AUG2017]

Template No: CS\_TP\_BS016 Revision 4  
Effective Date: 01Apr2016  
Reference: CS\_WI\_BS005

Copyright © 2009, 2010, 2012, 2016 Quintiles Transnational Corp. All rights reserved.  
The contents of this document are confidential and proprietary to Quintiles Transnational Corp. Unauthorized use, disclosure or reproduction is strictly prohibited.

TABLE AND LISTING MOCK SHELL

Listing 16.2.5  
 Study Medication  
 Full Analysis Population

Actual Treatment	Randomized Treatment	Subject ID/ Site ID/Age Group	Visit	Vaccination Date/Time (HH:MM)/Study Day	Arm of Administration	Treatment Deviation
Vaccine	Vaccine	xxxxx/ xxxx/ xxxx	Day 1	DDMMYYYY/HH:MM/ xx	Left	No
Vaccine	Vaccine	xxxxx/ xxxx/ xxxx	xxxxx	DDMMYYYY/HH:MM/ xx	Left	No
Vaccine	Vaccine	xxxxx/ xxxx/ xxxx	xxxxx	DDMMYYYY/HH:MM/ xx	Right	No

Study day: Derived relative to administration date/time of vaccination.  
 Please ensure that for all shells footnotes are relevant and complete

NOTE: in eCRF is Product Code which means that we will be able to check "actual" treatment. We have the RND number so we can check RND treatment if not as part of DS then at least here we need to show actual and randomized treatment and flag any deviations. Also please ensure this is clarified in the SAP.

Programming Note: Sort by Actual Treatment, Subject ID and Visit.

Document: \\IEEDC-NAS01A\Biosdata\Path\IVACFLU-S\IYA06804\Biostatistics \Documentation\SAP\IVACFLU-S-0203\_Mock\_Listings\_V1.0  
 Author: [name]  
 Version Number: 1.0  
 Version Date: [11AUG2017]

Template No: CS\_TP\_BS016 Revision 4  
 Effective Date: 01Apr2016

Reference: CS\_WI\_BS005

Copyright © 2009, 2010, 2012, 2016 Quintiles Transnational Corp. All rights reserved.  
 The contents of this document are confidential and proprietary to Quintiles Transnational Corp. Unauthorized use, disclosure or reproduction is strictly prohibited.

TABLE AND LISTING MOCK SHELL

Listing 16.2.6.1  
 Immunogenicity Result  
 Per-Protocol Population

Treatment	Subject ID/ Site ID/Age Group	Visit	Collection Date/Study Day	Antigens	HAI			
					Titer	Fold Increase (Day 22/Day 1)	>=1:40 Titer (Yes/No)	Seroconversion (Yes/No)
Vaccine	xxxxx/ xxxx/ xxxx	Day 1	DDMMYYYY/ xx	H1N1	xx	xx	Yes	Yes
		Day 22						
	xxxxx/ xxxx/ xxxx							
	xxxxx/ xxxx/ xxxx							

HAI: Hemagglutination Inhibition

Study day: Derived relative to administration date/time of vaccination.

Seroconversion is defined as a serum HAI antibody titer meeting the following criteria:

- Pre-vaccination titer <1:10 and a post-vaccination titer measured on Day 22 of ≥1:40 or
- Pre-vaccination titer ≥1:10 and at least a four-fold increase in post vaccination measured on Day 22

Programming Note: Sort by Treatment, Subject ID and Visit.

Document: \\IEEDC-NAS01A\Biosdata\Path\IVACFLU-S\IYA06804\Biostatistics \Documentation\SAP\IVACFLU-S-0203\_Mock\_Listings\_V1.0  
 Author: [name]  
 Version Number:  
 Version Date:

1.0  
 [11AUG2017]

Template No: CS\_TP\_BS016 Revision 4  
 Effective Date: 01Apr2016

Reference: CS\_WI\_BS005

Copyright © 2009, 2010, 2012, 2016 Quintiles Transnational Corp. All rights reserved.

The contents of this document are confidential and proprietary to Quintiles Transnational Corp. Unauthorized use, disclosure or reproduction is strictly prohibited.

TABLE AND LISTING MOCK SHELL

Listing 16.2.6.2  
 Immunogenicity Result- Antigens  
 Per-Protocol Population

Treatment	Subject ID	HAI (Titer)					
		H1N1		H3N2		B	
		Day 1	Day22	Day1	Day 22	Day 1	Day 22
Vaccine	xxxxx/ xxxx/ xxxx	xxx	xxx	xxx	xxx	xxx	xxx

HAI: Hemagglutination Inhibition

Programming Note: Sort by Treatment, Subject ID and Visit.

Document: \\IEEDC-NAS01A\Biosdata\Path\IVACFLU-S\IYA06804\Biostatistics \Documentation\SAP\IVACFLU-S-0203\_Mock\_Listings\_V1.0  
 Author: [name]  
 Version Number:  
 Version Date:

1.0  
 [11AUG2017]

Template No: CS\_TP\_BS016 Revision 4  
 Effective Date: 01Apr2016

Reference: CS\_WI\_BS005

Copyright © 2009, 2010, 2012, 2016 Quintiles Transnational Corp. All rights reserved.  
 The contents of this document are confidential and proprietary to Quintiles Transnational Corp. Unauthorized use, disclosure or reproduction is strictly prohibited.

TABLE AND LISTING MOCK SHELL

Listing 16.2.7.1  
 Solicited Local Reactogenicity  
 Full Analysis Population

Treatment	Subject ID/ Site ID/ Age Group	Temperature (°C)/ Finding	Grade of Temperature	Time Point	Solicited Local Adverse Events	Result			
Vaccine	xxxxx/ xxxx/ xxxx	Xx/Normal		30 Minute After Vaccination	Redness (cm) / Grade	Xx/ xx			
					Swelling (cm) / Grade	Xx/ xx			
					Induration (Hardness) (cm) / Grade	Xx/ xx			
					Pain	Xx			
							Day 1	Redness	Mild
								Swelling	None
								Hardness	Moderate
								Pain	xx
								Tenderness	xx
			Day 2						
			...						

CS: Clinically Significant; NCS: Not Clinically Significant;

Programming Note: Sort by Treatment, Subject ID and Time point.

Document: \\IEEDC-NAS01A\Biosdata\Path\IVACFLU-S\IYA06804\Biostatistics \Documentation\SAP\IVACFLU-S-0203\_Mock\_Listings\_V1.0  
 Author: [name]  
 Version Number:  
 Version Date:

1.0  
 [11AUG2017]

Template No: CS\_TP\_BS016 Revision 4  
 Effective Date: 01Apr2016

Reference: CS\_WI\_BS005

TABLE AND LISTING MOCK SHELL

Listing 16.2.7.2  
 Solicited Systemic Reactogenicity  
 Full Analysis Population

Treatment	Subject ID/ Site ID/ Age Group	Time Point	Solicited Systemic Adverse Events	Result
Vaccine	xxxxx/ xxxx/ xxxx	30 Minute After Vaccination	Fatigue/ Malaise	Mild
			Generalized Muscle Aches	Mild
			Joint Aches	Moderate
			Chills	Xxxx
			Nausea	Xxx
			Vomiting	Xxx
		Headache	xxxx	
		Day 1	Temperature (°C)	xxx
			Fatigue/ Malaise	Mild
			Generalized Muscle Aches	Mild
			Joint Aches	Moderate
			Chills	Xxxx
Nausea	Xxx			
Day 2	Vomiting	Xxx		
	Headache	xxxx		
	Temperature (°C)	xxx		
	Fatigue/ Malaise	Mild		
Generalized Muscle Aches	Mild			
...	...	...	...	

Programming Note: Sort by Treatment, Subject ID and Time point.

Document: \\IEEDC-NAS01A\Biosdata\Path\IVACFLU-S\IYA06804\Biostatistics \Documentation\SAP\IVACFLU-S-0203\_Mock\_Listings\_V1.0  
 Author: [name]  
 Version Number: 1.0  
 Version Date: [11AUG2017]

Template No: CS\_TP\_BS016 Revision 4  
 Effective Date: 01Apr2016  
 Reference: CS\_WI\_BS005

Copyright © 2009, 2010, 2012, 2016 Quintiles Transnational Corp. All rights reserved.  
 The contents of this document are confidential and proprietary to Quintiles Transnational Corp. Unauthorized use, disclosure or reproduction is strictly prohibited.

TABLE AND LISTING MOCK SHELL

Listing 16.2.7.3  
 Local and Systemic Solicited Reactogenicity by Maximum Severity between Day 1 to Day 7  
 Full Analysis Population

Treatment	Subject ID/ Site ID/ Age Group	Pain	Tenderness	Redness	Swelling	Hardness	Temperature (°C)	Fatigue/ Malaise	Muscle Aches	Joint Aches	Chills	Nausea	Vomiting	Headache
Vaccine	xxxxx/ xxxx/ xxxx	Mild	xxxx	xxx	xxxx	xxxx	Grade 0	Severe	xxx	xxx	xxx	xxx	xxxx	xxxx

Programming Note: Sort by Treatment and Subject ID.

Document: \\EEDC-NAS01A\Biosdata\Path\IVACFLU-S\IYA06804\Biostatistics \Documentation\SAP\IVACFLU-S-0203\_Mock\_Listings\_V1.0  
 Author: [name]  
 Version Number: 1.0  
 Version Date: [11AUG2017]

Template No: CS\_TP\_BS016 Revision 4  
 Effective Date: 01Apr2016  
 Reference: CS\_WI\_BS005

Copyright © 2009, 2010, 2012, 2016 Quintiles Transnational Corp. All rights reserved.  
 The contents of this document are confidential and proprietary to Quintiles Transnational Corp. Unauthorized use, disclosure or reproduction is strictly prohibited.

TABLE AND LISTING MOCK SHELL

Listing 16.2.7.4  
Unsolicited Adverse Events  
Full Analysis Population

Treatment	Subject ID/ Site ID/ Age Group	SOC/ Preferred Term/ Verbatim Term	Start Date/ End Date/ Study Day	Duration of AE (Days)	Severity/ Serious (Yes/No)	Relationship to Study Product	Action Taken/ Specification (e-CRF)	Outcome	Treatment Required (Yes/No)
Vaccine	xxxxx/ xxxx/ xxxx	Xxx/ xxxxx/ xxxx	DDMMYYYY/ DDMMYYYY/ xx	xx	Moderate/No	Not Related	None	Resolved	No

e-CRF: Electronic Case Report Form; MedDRA: Medical Dictionary for Regulatory Activities; SOC: System Organ Class  
Adverse Event terms were coded by SOC and Preferred Term using MedDRA version xx.x.  
Study day: Derived relative to administration date/time of vaccination.  
Duration is calculated based on start date and end date of AE.

Programming Note: Sort by Treatment, Subject ID, SOC and Preferred Term.

Document: \\IEEDC-NAS01A\Biosdata\Path\IVACFLU-S\IYA06804\Biostatistics \Documentation\SAP\IVACFLU-S-0203\_Mock\_Listings\_V1.0  
Author: [name]  
Version Number: 1.0  
Version Date: [11AUG2017]

Template No: CS\_TP\_BS016 Revision 4  
Effective Date: 01Apr2016

Reference: CS\_WI\_BS005

Copyright © 2009, 2010, 2012, 2016 Quintiles Transnational Corp. All rights reserved.  
The contents of this document are confidential and proprietary to Quintiles Transnational Corp. Unauthorized use, disclosure or reproduction is strictly prohibited.

TABLE AND LISTING MOCK SHELL

Listing 16.2.7.5  
 Serious Adverse Events  
 Full Analysis Population

Treatment	Subject ID/ Site ID/Age Group	SOC/ Preferred Term/ Verbatim Term	Start Date/ End Date/ Study Day	Duration of AE	Resolved Date	Serious Criteria	Severity	Relationship to Study Product	Outcome
Vaccine	xxxxx/ xxxx/ xxxx	Xxx/ xxxxx/ xxxx	DDMMYYYY/ DDMMYYYY/ xx	xx	DDMMYYYY	Death/ DDMMYYYY	Moderate	No	Resolved

SOC: System Organ Class;  
 Adverse Event terms were coded by SOC and Preferred Term using MedDRA version xx.x.  
 Study day: Derived relative to administration date/time of vaccination.

Duration is calculated based on start date and end date of AE.

Programming Note: Sort by Treatment, Subject ID, SOC and Preferred Term.

Document: \\EEDC-NAS01A\Biosdata\Path\IVACFLU-S\IYA06804\Biostatistics \Documentation\SAP\IVACFLU-S-0203\_Mock\_Listings\_V1.0  
 Author: [name]  
 Version Number: 1.0  
 Version Date: [11AUG2017]

Template No: CS\_TP\_BS016 Revision 4  
 Effective Date: 01Apr2016  
 Reference: CS\_WI\_BS005

Copyright © 2009, 2010, 2012, 2016 Quintiles Transnational Corp. All rights reserved.  
 The contents of this document are confidential and proprietary to Quintiles Transnational Corp. Unauthorized use, disclosure or reproduction is strictly prohibited.

TABLE AND LISTING MOCK SHELL

Listing 16.2.8.1  
Serum Collection  
Full Analysis Population

---

Treatment	Subject ID/ Site ID/Age Group	Visit	Sample Collected	Collection Date and Time/ Study Day
Vaccine	xxxxx/ xxxx/ xxxx	xxxx	Yes	DDMMYYYY/HH:MM/ xx
Vaccine	xxxxx/ xxxx/ xxxx	xxxxx	Yes	DDMMYYYY/HH:MM/ xx
Vaccine	xxxxx/ xxxx/ xxxx	xxxxx	Yes	DDMMYYYY/HH:MM/ xx

---

Study day: Derived relative to administration date/time of vaccination.

Programming Note: Sort by Treatment and Subject ID.

---

